- Removed hypothetical estimand for the co-primary endpoints and key secondary endpoints.
- Added two sensitivity analyses (one using multiple imputation and one using tipping point analysis) to the primary estimands for the co-primary endpoints.
- Added subgroup analysis based on ethnicity (Hispanic/Latino or Not Hispanic/Latino, Not Reported, and Unknown).

In addition, the following modifications were also made:

- Clarified the definition of baseline.
- Clarified when an adverse event is considered treatment emergent by adding a 4-week window after last dose or treatment discontinuation when evaluating safety for the 200 mg QD regimen. The same 4-week window rule applies to lab, vital sign and ECG data analyses.
- Clarified the calculations for PSSD symptom score and sign score.
- Clarified ECG analyses.
- Removed GenPs-SFQ analysis from Week 64 through Week 156.
- Noted that multiplicity adjusted p-values will be provided.
- Added safety summary through Week 52.
- Minor grammatical, formatting, or spelling changes were made.

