#### **4.5. Safety Analyses**

All safety analyses will be performed using safety analysis set based on actual intervention received. No formal statistical comparison is planned.

For all continuous safety variables, descriptive statistics by intervention group will include the N, mean, standard deviation, median, minimum, and maximum. Categorical variables will be summarized by intervention group using frequency counts and percentages.

The cumulative safety data will be analyzed through different study periods as shown below. Unless otherwise specified, tabular summaries of safety events are also presented as following:

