##### **Summary through Week 52 and /or through the reporting period (approximately the date when last participant finishing Week 52 visit):**

Safety data will be summarized by intervention group defined as follows:

- Placebo → JNJ-77242113: all participants who were randomized to placebo at Week 0, and later crossed over to receive treatment with JNJ-77242113 at or after Week 16. Only the safety events/measurements from these participants that occurred at or after Week 16 will be included.
- JNJ-77242113: Participants who were randomized to JNJ-77242113 at Week 0 and were treated with JNJ-77242113. All the safety events/measurements from these participants that occurred at or after Week 0 administration will be included in this group. However, safety events that occurred during the withdrawal period (on and after Week 28 and before retreatment) may be excluded for participants who were rerandomized to placebo at Week 24.
- Combined JNJ-77242113: all participant as described above in the Placebo → JNJ-77242113 and the JNJ-77242113 groups.

In addition, selected safety analysis from Week 24 through Week 52 may be performed among participants who were randomized to either receive placebo or continue to receive JNJ-77242113 at Week 24.

- Placebo (withdrawal): Participants who were randomized to JNJ-77242113 at Week 0, were PASI 75 or IGA 0 or 1 responders at Week 24, and rerandomized to placebo group at Week 24. Only the safety events/measurements from these participants that occurred at or after Week 24 randomization and before retreatment with JNJ-77242113 will be included in this group.
- Placebo → retreatment: Participants who were randomized to placebo at Week 24, started treatment with placebo, and retreated with JNJ-77242113 upon loss of 50% Week 24 PASI improvement. Only the safety events that occurred at or after their first retreatment of JNJ-77242113 will be included in this group.
- Placebo (combined 1 and 2 above): Participants who were randomized to placebo at Week 24. All safety events/measurements from these participants that occurred at or after Week 24 randomization will be included.
- JNJ-77242113 (Rerandomization): Participants who were randomized to JNJ-77242113 at Week 24 and continue to receive treatment with JNJ-77242113. All safety events occurred at or after Week 24 rerandomization will be included in this group.

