#### **4.5.2. Adverse Events**

The verbatim terms used in the CRF by investigators to identify adverse events will be coded using the MedDRA. In general, any AE occurring at or after the initial administration of study intervention up to 4 weeks after the last dose or treatment discontinuation is considered to be treatment emergent. If the event occurs on the day of the initial administration of study intervention, and either event time or time of administration are missing, then the event will be assumed to be treatment emergent. If the event date is recorded as partial or completely missing, then the event will be considered to be treatment emergent unless it is known to be prior to the first administration of study intervention based on partial onset date or resolution date. All reported treatment-emergent adverse events will be included in the analysis. For each adverse event, the

number and percentage of participants who experience at least 1 occurrence of the given event will be summarized by intervention group. The overall AEs will also be summarized by age group (adult, adolescent) and intervention group.

Summary tables will be provided for treatment-emergent adverse events:

- AEs
- Serious AEs (SAEs)
- AEs of Special Interest (AESIs)
- AEs leading to discontinuation of study intervention
- AEs of severe intensity
- AEs related to study intervention.
- AE of psoriasis

In addition to the summary tables, listings will be provided for participants who:

- Had SAEs
- Had AESIs
- Had AEs leading to discontinuation of study intervention
- Had AEs of severe intensity
- Had AE of psoriasis
- Had suicidal ideation or suicidal behavior
- Had serious hypersensitivity including anaphylactic reactions

A listing of participants who died will be provided.

Since safety should be assessed relative to follow-up, most AE summary tables will include average weeks of follow-up for each intervention group.

An AESI, which may be serious or non-serious, is an AE of scientific and medical concern specific to the sponsor's product or program, for which ongoing monitoring and expedited communication (within 24 hours) by the investigator to the sponsor is warranted. The AESIs for JNJ-77242113 are active TB, malignancy, and possible Hy's law cases.

A **possible Hy's law case** is defined by the occurrence of ALT/AST  $\geq 3 \times \text{ULN}$ , together with Tbili  $\geq 2 \times \text{ULN}$  or INR  $> 1.5$  (if measured).

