### 4.5.3. Additional Safety Assessments

#### 4.5.3.1. Clinical Laboratory Tests

Clinical laboratory tests will be displayed for the participants included in the safety analysis set.

Box plots of laboratory measurements and change from baseline will be provided for the select laboratory measurements. In addition, box plot for select laboratory measurements may be provided among adolescent participants.

Applicable laboratory results will be graded according to National Cancer Institute's Common Terminology Criteria for Adverse Events (NCI-CTCAE). The proportion of participants with post-baseline values by maximum toxicity grade for clinical laboratory tests will be summarized overall and by age group. Participants with toxicity grades  $\geq 2$  will be listed.

In addition, for selected laboratory parameters (i.e. ALT, AST), ULN will also be used to identify abnormal laboratory test results. Lipid and hs-CRP will be summarized. The 4-week window after the last dose or treatment discontinuation will be applied.

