#### 4.5.3.2. Vital Signs

Vital signs and change from baseline will be summarized over time. Incidence of treatment-emergent markedly abnormal vital signs during intervention, as defined in [Table 8](#), will be summarized for participants who had a baseline assessment and at least 1 postbaseline assessment for that vital sign. A listing of participants with treatment-emergent markedly abnormal vital signs will be presented. The 4-week window after the last dose or treatment discontinuation will be applied.

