#### **4.5.3.6. Electrocardiogram**

The Electrocardiogram data will be summarized by ECG parameter. Descriptive statistics will be calculated at baseline and for observed values and change from baseline at each scheduled time point.

In addition, summary of post-baseline ECG abnormalities different from Week 0 and a listing of subjects with any post-baseline ECG abnormalities different from Week 0 measurement will be provided. The 4-week window after the last dose or treatment discontinuation will also be applied.

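### The Week 52 JNJ-77242113 safety column has no firm rule removing data from adults on withdrawal placebo: PHQ-9 and C-SSRS values stay in, and the 4-week window for laboratory, vital-sign and ECG data has an undefined starting point

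*SAP*

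**What the plan says.** SAP 4.5 first sets the general rule: "All safety analyses will be performed using safety analysis set based on actual intervention received". For the summary through Week 52 it then defines the JNJ-77242113 group as those randomized to and treated with JNJ-77242113 from Week 0, and adds: "All the safety events/measurements from these participants that occurred at or after Week 0 administration will be included in this group". The Combined JNJ-77242113 group takes this group over whole.

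The exception for adults re-randomized to placebo at Week 24 follows directly: "However, safety events that occurred during the withdrawal period (on and after Week 28 and before retreatment) may be excluded".

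Other SAP sections add a time limit for some data types:

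- **Adverse events (4.5.2):** treatment emergence covers "any AE occurring at or after the initial administration of study intervention up to 4 weeks after the last dose" or treatment discontinuation.
- **Laboratory (4.5.3.1):** "The 4-week window after the last dose or treatment discontinuation will be applied". Vital signs (4.5.3.2) carry the same sentence.
- **ECG (4.5.3.6):** "The 4-week window after the last dose or treatment discontinuation will also be applied".
- **C-SSRS (4.5.3.3) and PHQ-9 (4.5.3.5):** no window. C-SSRS is summarized by the most severe post-baseline outcome through each reporting period, including the one at the Week 52 database lock. PHQ-9 is summarized by a shift table.

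The SAP's summary of changes describes the window as "adding a 4-week window after last dose or treatment discontinuation when evaluating safety for the 200 mg QD regimen". It lists laboratory, vital-sign and ECG data as also covered, and does not list PHQ-9 or C-SSRS.

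**The concern.** Adults re-randomized to placebo at Week 24 are off drug until they relapse or reach Week 52. A column labelled JNJ-77242113 should not carry their off-drug data without saying so. As written, the default is to include everything. The one exception is discretionary and narrower than the default: the default speaks of events and measurements, the exception of events only.

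What is at stake is how the long-term safety tables read. An abnormal value that arises on placebo can be attributed to the drug. For C-SSRS one off-drug assessment can set a participant's category, because the table takes the worst post-baseline outcome. The word *may* also leaves the choice open after the Week 24 lock, when Protocol 6.4 lets selected sponsor staff see the randomization codes.

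**Working it through.** **1. Size of the affected group.** Inputs from SAP 1.2 and SAP 5: about 540 adults, 2:1 allocation, 75% PASI 75 responders at Week 24, 1:1 re-randomization, and 400 participants on JNJ-77242113 at Week 0.

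- Adults on JNJ-77242113: 540 × 2/3 = 360
- Re-randomized: 360 × 0.75 = 270
- To placebo: 270 / 2 = 135, which matches the n = 135 per arm in SAP Table 9
- Share of the column: 135 / 400 = 33.8%
- Share of the combined column, if all 200 placebo participants cross over: 135 / 600 = 22.5%

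As a check on that n, the pooled-variance two-proportion power formula with 135 per arm and two-sided 0.05 gives 95.2%, 97.0% and 98.7%. The SAP states 95.2%, 97.0% and 98.6%. Nothing in this point alters those figures. Adults who qualify for re-randomization on IGA alone are not counted in the 135, so the true number could be slightly higher.

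**2. PHQ-9 and C-SSRS values exposed.** Protocol 1.3.1 schedules both at 12 post-baseline visits through Week 52 (Weeks 2, 4, 8, 12, 16, 20, 24, 28, 32, 36, 44, 52). Five of them fall on or after Week 28, the SAP's own cut-off.

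- Scheduled values in the column, per scale: 400 × 12 = 4,800
- Upper bound of off-drug values: 135 × 5 = 675, and 675 / 4,800 = 14.1%

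The documents give no retreatment rate. If 20% to 60% of those five visits fall after retreatment (an assumption):

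| Visits after retreatment | Off-drug values | Share of 4,800 |
|---|---|---|
| 0% | 675 | 14.1% |
| 20% | 540 | 11.3% |
| 40% | 405 | 8.4% |
| 60% | 270 | 5.6% |

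**3. Does the 4-week window close the gap for laboratory, vital-sign and ECG values?** It depends on which dose is the last one.

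- *Last JNJ-77242113 dose before withdrawal.* Week 24 + 4 = Week 28, so later off-drug values leave the column. This is the only reading that works, and no operative section states it.
- *Last dose of study intervention.* Protocol 6.1 lists placebo as investigational product and withdrawn adults keep taking it, so the window does not close at Week 28. SAP 4.5.1 likewise computes exposure from first to last day of study medication with no gap subtracted.
- *Last JNJ-77242113 dose overall.* Under SAP 1.2 withdrawn adults restart at relapse or at Week 52. Once they restart, this dose lies after the off-drug gap, and a window running beyond it does not remove the gap.

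**4. Consistency.** The adverse-event definition already carries the 4-week window. If that window removed post-Week 28 data, the optional exclusion in SAP 4.5 would be redundant, and a mandatory window would contradict *may*. The passages need reconciling on either reading.

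**The case against.** The strongest reply is that the SAP's intent is visible. The window serves the 200 mg QD regimen, its arithmetic lands on Week 28, and SAP 4.5 uses the same Week 28 cut-off. On that reading laboratory, vital-sign and ECG values are already handled. A reader who stops at the opening statement of the vital-signs section, "Vital signs and change from baseline will be summarized over time", might infer that the column keeps all such values from withdrawn adults. The documents do not support that, because the same section and its laboratory and ECG counterparts end with the window. What remains is that the purpose appears only in the summary of changes, while the operative sections leave the last dose undefined.

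A second reply is that the SAP uses the term safety events loosely. Two other groups in the same list (Placebo to retreatment, and the JNJ-77242113 rerandomization group) also mention only events, and read literally they would hold no laboratory data at all. This is fair: the omission may be drafting rather than a decision to keep measurements. It is still not a rule that a programmer can follow.

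Third, the consequences are bounded. No formal safety comparison is planned and the Week 16 and Week 24 summaries precede withdrawal. ECG, lipids and hs-CRP are scheduled only at Week 52 in this period. A Placebo (withdrawal) group covering events and measurements is already defined. All of this stands, except that the analysis by that group is itself described as selected and optional.

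**Conclusion.** The point holds in this form. For PHQ-9 and C-SSRS, following the text places off-drug values in the JNJ-77242113 and combined columns, contrary to the actual-intervention rule. This concerns about 135 of 400 participants (34%) and at most about 14% of scheduled post-baseline values per scale in the JNJ-77242113 column, or roughly 6% to 11% if 20% to 60% of the visits follow retreatment. For laboratory, vital-sign and ECG values the result depends on a definition that the SAP does not give. For adverse events the exclusion is optional.

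A reader might go further and put a figure on how much a mean drug effect is diluted in the column. The documents do not support one: it would rest on retreatment rates they do not contain, and it has no meaning for shift tables or maximum-score tables, where an added record can change a category but there is no mean to dilute.

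The 135 and 400 are planning numbers, and the 14% assumes every scheduled visit is attended. No efficacy analysis, sample size or power figure changes. This is more than missing detail, because it decides what the long-term JNJ-77242113 safety columns report.

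**What to change.** In SAP 4.5, replace the optional sentence with a mandatory rule:

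> For participants re-randomized to placebo at Week 24, safety events and measurements (laboratory, vital signs, ECG, PHQ-9, C-SSRS) occurring more than 4 weeks after the last JNJ-77242113 dose before withdrawal and before the first retreatment dose will be excluded from the JNJ-77242113 and Combined JNJ-77242113 columns and shown in the Placebo (withdrawal) group.

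Use the same starting point, the last JNJ-77242113 dose before withdrawal, wherever the 4-week window appears (SAP 4.5.2, 4.5.3.1, 4.5.3.2 and 4.5.3.6). Because the excluded data must appear somewhere, the Placebo (withdrawal) summary should become a planned rather than optional output.

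The cost is SAP wording and one period flag in the safety datasets. The JNJ-77242113 column will hold fewer records at Weeks 28 to 52.

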#### **Summary through Week 160:**

- Safety data through Week 160 will be summarized for participant exposure to JNJ-77242113.

#### **4.5.1. Extent of Exposure**

The extent of exposure will be summarized for randomized participants who received at least one study agent administration. Distribution of study agent lot will be summarized over time. Descriptive statistics for the average daily dose of study intervention and duration of exposure to study medication (weeks) will be summarized.

Total duration of exposure = last day of study medication - first day of study medication + 1.

Study intervention compliance will be summarized descriptively. See Appendix 6.6 for further details.

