6. STUDY INTERVENTION AND CONCOMITANT THERAPY

6.1. Study Intervention(s) Administered

The study intervention will be provided as tablets for oral administration.

For adult participants:

For adult participants, the study intervention must be swallowed whole. Participants will be instructed to take the study intervention at approximately the same time every day upon waking with 240 mL (8 oz) water on an empty stomach (no food intake for at least 2 hours before and for at least 30 minutes after taking the study intervention).

For adolescent participants:

For adolescent participants, the participant's legal guardian or caregiver may assist with administration of the study intervention.

For adolescent participants, the study intervention should be swallowed whole. Adolescent participants will be instructed to take the study intervention at approximately the same time every day upon waking with 240 mL (8 oz) water on an empty stomach (no food intake for at least 2 hours before and for at least 30 minutes after taking the study intervention).

If adolescent participants have difficulty swallowing tablets, the study intervention may be suspended in a glass of water and taken within 15 minutes. It may take a few minutes for the tablet to fully disperse. The tablet may not disperse completely (milky to cloudy appearance), and small pieces may be seen in the water and are safe to swallow. After drinking the study intervention, rinse and swirl the glass with more water and swallow to ensure all the study intervention is taken. The total amount of water to be used for the dispersion of the tablet and rinsing should be at least 240 mL (about 8 oz or 1 cup).

Study personnel should review dose administration requirements with the participant, as appropriate, and with the delegated caregiver(s) before administration and throughout the study as necessary.

Designation	Product			
Investigational Medicinal Product(s)	JNJ-77242113, placebo for JNJ-77242113			
	Authorization status in the EU/EEA			
	
 
 Authorized	Not applicable	
 
 Unauthorized	JNJ-77242113, placebo for JNJ-77242113	
 
	Authorized	Not applicable	Unauthorized
Authorized	Not applicable			
Unauthorized	JNJ-77242113, placebo for JNJ-77242113			
NIMP/AxMP	Not applicable			

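### The SAP's only exposure formula counts off-drug time, so it does not measure JNJ-77242113 exposure at Weeks 52 and 160 or match the windows in which adverse events are counted

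*SAP*

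**What the plan says.** SAP 4.5.1 has one exposure definition: "Total duration of exposure = last day of study medication - first day of study medication + 1". The summary it feeds is worded in terms of study medication, not active drug: "Descriptive statistics for the average daily dose of study intervention and duration of exposure to study medication (weeks) will be summarized". Protocol 6.1 names the investigational products as "JNJ-77242113, placebo for JNJ-77242113", so placebo tablets are study medication.

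SAP 4.5 sets the event windows for the summary through Week 52 by group:

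- Placebo → JNJ-77242113: "Only the safety events/measurements from these participants that occurred at or after Week 16 will be included".
- JNJ-77242113: events count from Week 0, but for those re-randomized to placebo at Week 24, "safety events that occurred during the withdrawal period (on and after Week 28 and before retreatment) may be excluded".
- A Placebo (withdrawal) group is defined from Week 24 to retreatment, within a selected analysis that is itself optional.

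The summary through Week 160 is to be based on exposure to JNJ-77242113. The SAP defines exposure nowhere except in 4.5.1.

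SAP 4.5.2 reports frequency per participant: "number and percentage of participants who experience at least 1 occurrence of the given event will be summarized by intervention group". It adds that "most AE summary tables will include average weeks of follow-up for each intervention group". That follow-up is not defined, and no exposure-adjusted rate is planned.

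**The concern.** Two groups spend planned time off active drug: the placebo arm in Weeks 0 to 16, and adults withdrawn at Week 24 until retreatment or Week 52. The formula is a calendar span, so it has no means of leaving out a gap between first and last dose. Reading study medication as JNJ-77242113 alone does not fully cure this, because a retreated participant's off-drug gap still lies inside the span.

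The event windows do leave out some of that time. Events and time therefore run on different clocks, and the programmer has no written rule to reconcile them.

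SAP Section 5 says the sample size was also chosen to give a reasonable safety database, and SAP 4.5.2 itself says safety should be judged relative to follow-up. At stake is whether the reported duration of exposure, and the follow-up printed beside the adverse event counts, describe time on JNJ-77242113.

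The optional wording of the exclusion adds a further problem. Under Protocol 6.4, selected sponsor staff receive the randomization codes after the Week 24 lock. As written, the choice to exclude could be made with the codes known.

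**Working it through.** **Inputs.** 540 adults and 60 adolescents, randomized 2:1, giving 400 and 200 (SAP 1.2 and 5). 75% of the adult JNJ-77242113 arm is assumed to be re-randomized, 1:1 (SAP 5). Crossover is at Week 16; withdrawal runs from Week 24 to Week 52 at most. Time to retreatment is not given, so mean weeks off drug, *w*, is an assumption shown from 4 (the first scheduled visit after Week 24 is Week 28) to 28. Dropout is set to zero.

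**The plan's own figures.** Withdrawn: 540 × 2/3 × 0.75 / 2 = 135, which matches SAP Table 9. With n = 135 per group, two-sided 0.05 and pooled variance under the null, power for 60% vs 80% is Φ[(0.20 − 1.96·√(2 × 0.7 × 0.3/135)) / √((0.24 + 0.16)/135)] = Φ(1.67) = 95.2%, as stated. The other two rows give 97.0% and 98.7% (stated 97.0% and 98.6%). The documents state no exposure total.

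**Span against on-drug time, JNJ-77242113 group, through Week 52.** Span = 400 × 52 = 20,800 person-weeks. On-drug = 20,800 − 135*w*.

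| *w* (weeks) | Off drug | On drug | Span too long by |
|---|---|---|---|
| 4 | 540 | 20,260 | 2.7% |
| 8 | 1,080 | 19,720 | 5.5% |
| 12 | 1,620 | 19,180 | 8.4% |
| 16 | 2,160 | 18,640 | 11.6% |
| 28 | 3,780 | 17,020 | 22.2% |

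At *w* = 28 the mean is 52.0 weeks by formula against 42.5 on drug. That top end needs the literal reading, with placebo tablets counted. If only JNJ-77242113 doses counted, a participant not yet retreated would have a last dose near Week 24 at the Week 52 cut. Anyone retreated earlier would still have the gap counted, and in the Week 160 summary so would everyone who resumed at Week 52.

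**Crossover and combined groups, if the clock starts at the first placebo tablet.** Crossover: 52/36 − 1 = 44.4%. Combined span = 600 × 52 = 31,200. Combined on-drug = 20,800 − 135*w* + 200 × 36, which is 27,460 at *w* = 4 (span 13.6% too long) and 24,220 at *w* = 28 (28.8%).

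**Follow-up against counted events.** If the exclusion is applied, it removes *w* − 4 weeks per withdrawn participant. Counted time = 20,800 − 135(*w* − 4): 20,800 at *w* = 4 and 17,560 at *w* = 28. If average follow-up still uses 20,800, events per unit of follow-up are understated by 1 − 17,560/20,800 = 15.6% at most, and by 0% at *w* = 4.

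**Effect on adverse event percentages.** From the formula, none: the denominator is participants. From the exclusion there can be an effect, because all 400 stay in the denominator. As an illustration, assume a constant 0.5 first events per person-year. The expected percentage is [265·P(52) + 135·P(52 − (*w* − 4))]/400, with P(t) = 1 − exp(−0.5t/52.18). It is 39.2% with nothing excluded, 37.6% at *w* = 12 and 33.9% at *w* = 28.

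**The case against.** The strongest reply is that 4.5.1 never claims to measure JNJ-77242113 exposure. It measures time on blinded study medication, and for that it is correct. Safety analyses are by intervention actually received, and the SAP does not say that the crossover group's clock starts at the first placebo tablet. That stands in part: the 44% and the combined-group range depend on a reading that the SAP leaves open. It does not dispose of the point, because the Week 160 summary relies on JNJ-77242113 exposure and no other definition exists.

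Three stronger inferences are tempting, and the documents do not support them:

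- *That the formula dilutes adverse event frequency.* The planned frequencies are percentages of participants, and the 4.5.1 span enters none of them.
- *That person-year totals or counts of participants exposed for a year are inflated.* The SAP plans neither output.
- *That the main randomized safety comparison is affected.* Through Week 16 neither arm is scheduled to change treatment.

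The exclusion also has a rationale. Week 28 is Week 24 plus the 4-week window in SAP 4.5.2, and removing later off-drug events from an active-drug column is reasonable. Serious events, events of special interest and deaths are listed in any case, and psoriasis rebound is assessed separately. What remains is that the exclusion is discretionary, the withdrawal column that would show the removed events is only optional, and no rule shortens follow-up to match.

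**Conclusion.** The point holds as a mismatch between the time base and the event windows. For the Week 52 and Week 160 summaries, the one exposure formula in the SAP does not give time on JNJ-77242113. The excess in the JNJ-77242113 group through Week 52 runs from small to about a fifth, depending almost entirely on how long withdrawn participants stay off drug, which the documents do not state. The larger crossover and combined figures are conditional on when that group's clock starts. All figures assume no dropout and 135 withdrawn.

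The follow-up issue is separate and also conditional. The understatement of up to about 16% arises only if the exclusion is applied and the undefined average follow-up includes the excluded weeks. Nothing here shows that a planned adverse event percentage is wrong because of the exposure formula. The plan should still be changed: it leaves the choice of clock, and the choice to exclude, to be settled after the SAP is final.

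**What to change.** For the Week 52 and Week 160 JNJ-77242113 summaries:

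1. Define exposure as the sum of intervals on JNJ-77242113. For crossover participants, start at the first JNJ-77242113 dose at or after Week 16. For withdrawn participants, use Week 0 to Week 24 plus time from the first retreatment dose. The study-medication span can stay as a separate, clearly labelled summary.
2. Compute average follow-up over the same window in which events are counted: on-drug time plus the 4-week window.
3. Replace the optional exclusion with a fixed one, and commit to tabulating the removed events in the Placebo (withdrawal) group.
4. Add exposure-adjusted incidence per 100 person-years to the Week 52 and Week 160 tables, where follow-up differs by design (36 against 52 weeks through Week 52).

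The cost is SAP wording and some extra programming from dosing dates already collected. The exposure figures will look less favourable.
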